1.0 STUDY SUMMARY

Hepatitis B is a vaccine-preventable viral infection causing substantial morbidity and mortality. In 2015, there were an estimated 21,900 new acute cases and up to 2.2 million people living with chronic hepatitis B disease in the U.S. ^[1]. Hepatitis B vaccination is recommended for adults at risk through sexual exposure, percutaneous or mucosal exposure, travelers, and those with hepatitis C infection, HIV infection, or diabetes mellitus ^[2, 3]. Available hepatitis B vaccines require 3 doses over 6 months, but coverage has been low (eg, <25% of persons with diabetes in 2015) ^[4].

HEPLISAV-B is a hepatitis B vaccine developed by Dynavax, comprised of recombinant yeast cell-derived hepatitis B surface antigen (HBsAg) and a proprietary 22-mer phosphorothioate oligodeoxynucleotide adjuvant, 1018^[5]. HEPLISAV-B vaccine is approved for prevention of hepatitis B virus infection in adults aged 18 years and older. HEPLISAV-B induced higher and earlier seroprotection than comparator vaccine Engerix-B[®] in Phase 3 trials, and requires only 2 doses over 1 month. In pre-licensure clinical trials, the rates of serious adverse events and events leading to study discontinuations were similar between HEPLISAV-B and Engerix-B, except for a numerical imbalance in events coded with the Medical Dictionary for Regulatory Activities (MedDRA) preferred term of acute myocardial infarction (AMI) in a single trial, HBV-23 (HEPLISAV-B: 0.25% [n = 14]; Engerix-B: 0.04% [n = 1])^[6]. Based on a comprehensive assessment, the observed numerical difference between treatment groups in the occurrence of events coded to the MedDRA preferred term acute myocardial infarction in HBV-23 is an isolated finding in the HEPLISAV-B database that appears most likely explained by random variation resulting in an unexpectedly low number of events observed in the Engerix-B group in HBV-23. This observational post-marketing surveillance study is being conducted to confirm the lack of association of HEPLISAV-B with myocardial infarction and cardiovascular outcomes.

This observational surveillance study will take place at Kaiser Permanente Southern California (KPSC), a large integrated health care organization serving approximately 4.4 million highly diverse members. KPSC has extensive experience in vaccine safety and effectiveness studies. In this non-randomized cluster design, HEPLISAV-B will be used exclusively at approximately 7 medical centers while another hepatitis B vaccine will be used exclusively at 8 other medical centers. Approximately 25,000 adult patients will receive HEPLISAV-B and approximately 25,000 adult patients will receive the comparator vaccine. Patients will be followed for occurrence of AMI through their electronic health records for 13 months.

The occurrence of AMI in patients who receive at least 1 dose of HEPLISAV-B will be compared with patients who receive at least 1 dose of the comparator hepatitis B vaccine. The number of vaccines administered and the number of suspected (unconfirmed) AMI will be

Dynavax Technologies Corporation HEPLISAV-B $^{\textcircled{B}}$

reported. Two interim comparisons of unconfirmed AMIs between vaccine groups will be conducted. The final analysis will be based on a Cox proportional hazards model employing inverse probability of treatment weighting (IPTW). Potential confounding factors with respect to cardiovascular disease risk factors in the use of the 2 vaccines will be adjusted for in data analyses. An independent data monitoring committee (DMC) will review interim and final analyses.

2.0 INTRODUCTION

Hepatitis B is a viral infection causing substantial morbidity and mortality. In 2015, there were an estimated 21,900 new acute cases, and an estimated 850,000 to 2.2 million people living with chronic hepatitis B disease in the U.S., with many unaware of infection ^[1]. The risk of developing chronic disease after infection is 90% in infants, 25% to 50% in children, and 6% to 10% in adults ^[7, 8]. Asian Americans and Pacific Islanders comprise more than half of Americans living with chronic hepatitis B. Approximately 1% of acute hepatitis B infections result in liver failure and death, and of those with chronic disease, 15% to 25% are at risk of death from cirrhosis or hepatocellular carcinoma ^[9-12].

Most new infections of hepatitis B are in adults ages 30 years and older, as the younger population has been largely protected since 1991 with universal hepatitis B vaccination of infants and catch up vaccination of adolescents ^[1, 13]. Hepatitis B vaccination has been recommended since 1981 for adults at higher risk of exposure, including sexual exposure (unprotected sex with an infected partner, multiple sexual partners, men who have sex with men); percutaneous or mucosal exposure (injection drug use, chronic kidney disease, healthcare workers); travelers to countries with a high prevalence of hepatitis B; and persons with chronic liver disease, hepatitis C, or human immunodeficiency virus ^[2]. As persons with diabetes mellitus have an increased risk of exposure if diabetes-care equipment is shared, they should be vaccinated for hepatitis B if younger than 60 years of age ^[3, 4].

Approved single-antigen hepatitis B vaccines for adults include Recombivax HB (Merck) and Engerix-B (GlaxoSmithKline)^[14]. These are comprised of recombinant hepatitis B surface antigen (HBsAg) with an aluminum salt adjuvant and require 3 doses over 6 months. Coverage of hepatitis B vaccination has remained low in adults. In 2015, 24.6% of adults age 19 years or older were vaccinated with at least 3 doses. Among persons with diabetes ages 19-59 years of age, 24.4% were vaccinated with at least 3 doses ^[15, 16].

Dynavax has developed HEPLISAV-B for hepatitis B vaccination of adults. HEPLISAV-B is a hepatitis B vaccine comprised of recombinant yeast cell-derived HBsAg and a proprietary 22-mer phosphorothioate oligodeoxynucleotide adjuvant, 1018^[5]. Two doses of HEPLISAV-B are

required, with the second dose 1 month after the first; this schedule may reduce barriers and improve vaccination coverage of adults. Furthermore, HEPLISAV-B has demonstrated significantly greater and earlier seroprotection compared to Engerix-B, including in persons with diabetes.

Safety data from adults who received at least 1 dose of HEPLISAV-B in pre-licensure clinical trials have demonstrated a similar safety profile when compared to the licensed hepatitis B vaccine, Engerix-B. Adverse events were generally mild and infrequent. The rates of serious adverse events and events leading to study discontinuations were also similar between HEPLISAV-B and Engerix-B except for a numerical imbalance in events coded with the Medical Dictionary for Regulatory Activities (MedDRA) preferred term of *acute myocardial infarction* (AMI) in a single trial, HBV-23 (HEPLISAV-B: 0.25% [n = 14]; Engerix-B: 0.04% [n = 1]). The myocardial infarctions occurred in subjects in whom such events would be expected based on their high prevalence of baseline cardiovascular risk factors, occurred randomly with no temporal relationship to time of vaccine administration, occurred at lower than expected incidence rates, and were not related to a persistent inflammatory state or an autoimmune condition ^[6]. Based on the totality of the data, the imbalance was most likely due to random variation in the small number of events reported but did not unequivocally prove no increase in risk. However, this risk of acute myocardial infarction will be monitored in the post-marketing observational surveillance study described in this protocol.

3.0 OBJECTIVE

The primary objective of this post-marketing observational surveillance study is to compare the occurrence of AMI in recipients of HEPLISAV-B with recipients of another hepatitis B vaccine.

4.0 STUDY DESIGN

4.1 Study Setting

This study will be conducted by Kaiser Permanente Southern California (KPSC). KPSC is a large integrated health care organization and represents the largest Kaiser Permanente region in the U.S. KPSC spans a vast geographic area, covering a distance of over 230 miles between Bakersfield in the north and San Diego in the south. KPSC has over 7,000 physicians, 15 hospitals and 225 medical offices and serves approximately 4.4 million members with diverse ethnic and socioeconomic backgrounds largely representative of the underlying population ^[17]. Health plan members enroll through their employer or a family member's employer, through individual and family plans, or through state or federal programs. KPSC utilizes a comprehensive electronic health record system to track members' healthcare encounters.

The KPSC Center for Vaccine Safety and Effectiveness Research conducts research with realworld implications. In partnership with clinicians, academics, federal funders (eg, the Centers for Disease Control and Prevention, the U.S. Food and Drug Administration (FDA), and the National Institutes of Health), and industry sponsors, investigators conduct a wide range of studies, from the incidence and outcomes of vaccine-preventable disease to the safety and effectiveness of vaccines. Published studies include the post-licensure safety of measles, mumps, rubella, varicella vaccine (MMRV)^[18], autoimmune conditions following quadrivalent human papillomavirus vaccine ^[19], safety of quadrivalent meningococcal conjugate vaccine ^[20], safety of zoster vaccine in the Vaccine Safety Datalink (VSD) ^[21], and hepatitis B testing and vaccination ^[22]. In addition, KPSC has used a modern advanced method, inverse probability of treatment weighted (IPTW) estimation, to adjust for potential selection bias in observational studies, including a study of the safety of testosterone replacement based on cardiovascular outcomes ^[23] and an evaluation of the safety of seasonal influenza vaccine among hospitalized surgical patients ^[24].

The KPSC Regional Immunization Practice Committee (RIPC) makes recommendations to ensure appropriate use of vaccination and implementation of new Advisory Committee on Immunization Practices (ACIP) recommendations within medical centers. KPSC has a proactive immunization program that includes: 1) alerts on the electronic health record that indicate which vaccines are due; 2) a policy of vaccinating at all visits, not just well visit or physical exam appointments; and, 3) giving recommended immunizations on a walk-in basis without appointment at no-cost nurse visits. Since all ACIP-recommended immunizations are free to members at any visit regardless of co-pay status, there is an incentive to receive immunizations within the KPSC system.

KPSC maintains comprehensive electronic health records to integrate medical information including diagnosis and procedure codes, immunizations, medications and laboratory results from outpatient, emergency department (ED), and inpatient settings within the KPSC network. All details of a patient encounter are entered into the electronic health record at the point of care. Events are coded using standard *International Classification of Diseases* (ICD) codes. Events occurring in the outpatient setting are captured directly from provider input. Those in the emergency department and inpatient settings are coded by professional coders, based on review of the health record. There is strong incentive for KPSC members to seek care within the health plan system; however, members may seek emergency medical care from outside healthcare providers. For outside facilities to be reimbursed, claims must include documentation substantiating a clinical diagnosis, which is entered into administrative data systems. In addition, KPSC is part of the Care Everywhere Network, which facilitates sharing of health records between organizations using the Epic electronic health record system. Thus, the capture of care delivered to KPSC members by electronic data is comprehensive.

4.2 Overview of Study Design

This is an observational surveillance study of adults aged 18 years and older who are enrolled in KPSC and receive a hepatitis B vaccination during the study period. This design will provide real world evidence on the risk of AMI in a highly diverse population vaccinated with HEPLISAV-B. Approximately 25,000 patients will receive HEPLISAV-B and approximately 25,000 patients will receive another hepatitis B vaccine according to a non-randomized cluster design. HEPLISAV-B will be used exclusively at approximately 7 medical centers in family practice and internal medicine departments, while another hepatitis B vaccine will be used exclusively at the other 8 medical centers in family practice and internal medicine departments. For each patient, the index dose is defined as the first dose of HEPLISAV-B during the study vaccination period given in family practice and internal medicine departments at medical centers assigned to the HEPLISAV-B cohort, or the first dose of hepatitis B comparator vaccine (non-dialysis formulation) during the study vaccination period given in family practice and internal medicine departments at medical centers assigned to the comparator cohort. Each individual patient will be passively followed through their electronic health records for 13 months after the index vaccine dose during the study period. The occurrence of AMI in patients who receive at least 1 dose of HEPLISAV-B at the medical centers in the HEPLISAV-B arm will be compared with patients who receive at least 1 dose of another hepatitis B comparator vaccine at medical facilities in the comparison arm. Hospitalized AMI events, based on International Classification of Diseases, 10th Revision, Clinical Modification (ICD-10-CM) predefined codes (Appendix 1), will be identified from electronic health records from inpatient care. The electronic health records of potential AMI events will be abstracted and redacted of hepatitis B vaccination information. Events will be independently adjudicated by two cardiologist reviewers masked to the vaccine exposure, with a third cardiologist to review cases with differing conclusions.

4.3 Selection of Target Medical Centers

To reduce potential selection bias resulting from physician's or patient's decisions based on a patient's risk profile, HEPLISAV-B will be provided to selected medical centers as the sole vaccine for adult use in routine clinical care in family practice and internal medicine departments. Thus, providers and patients will rarely have a choice of hepatitis B vaccines, emulating a non-randomized clustered design. HEPLISAV-B will be provided exclusively to approximately 7 medical centers for adult use in their affiliated family practice and internal medicine departments. The remaining 8 medical centers and affiliated family practice and internal medicine departments will continue to use their current hepatitis B vaccine exclusively.

Site selection for the study is based on clustering of medical centers and logistics. The electronic health record in KPSC is supported in clusters of medical centers. Each medical center consists of a hospital and associated medical office buildings. When alerts or order sets are created or modified in the electronic health record, they are usually done across all clusters. In the case of this study, changes will be made in select clusters but not others, with the order sets for adult hepatitis B vaccine for family practice and internal medicine departments changed from the current vaccine to HEPLISAV-B. Target medical centers are also selected based on their proximity to our regional research headquarters in Pasadena, since study staff will need to travel to train and monitor clinic staff in HEPLISAV-B vaccine management activities, as is standard conduct for any new vaccine. We will also select the medical centers in which our clinical investigators work so that they can serve as advocates and points of contact for clinical staff.

Prior to initiation of the study, vaccine management (eg, procurement of non-formulary vaccine) and training activities will be conducted for target medical centers including educational and operational outreach. During the study, regular vaccine uptake reports will be generated as well as monitoring of the proper usage and administration of HEPLISAV-B through standard vaccine management operations.

Overall, the rate of adult hepatitis B vaccination at the target medical centers has been similar to those in the comparator medical centers (Table 4-1). In 2015, approximately 55% overall were age 50 years or older. Recipients at target and comparator medical centers were similar in terms of age distribution, sex, history of diabetes and history of AMI. There were modest differences by race/ethnicity. The recipients in both the target and comparator medical centers had similar risk of AMI in the 12 months following the first hepatitis B vaccination. Across both cohorts, approximately 45% of persons with AMI were identified through claims submitted for care delivered outside of KPSC facilities.

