4.4 Study Period

The study will begin with administration of the first dose of HEPLISAV-B and is contingent upon ACIP and RIPC recommendation of HEPLISAV-B. The study vaccination period will occur until 25,000 patients have received at least 1 dose of HEPLISAV-B, expected to take approximately 10.5 months based on historical vaccination trends. Each patient will be followed until the earliest of disenrollment from KPSC (not due to death and allowing for a 31-day gap in membership), death from any cause, or the end of the 13-month follow-up period after the index dose given during the vaccination period.

Table 4-1:Adult Hepatitis B Vaccine Recipients: Active Member at First Dose
Date, 2015 by Target (HEPLISAV-B) and Comparator Medical
Centers

	8 Comparator	7 Target	Total
	Medical Centers	Medical Centers	
N	47,964	45,766	93,730
Age (years)			
Mean (SD)	49.1 (10.83)	49.0 (10.90)	49.1 (10.86)
Sex	n (%)	n (%)	n (%)
Female	23,229 (48.43)	22,400 (48.94)	45,629 (48.68)
Male	24,735 (51.57)	23,366 (51.06)	48,101 (51.32)
Race/Ethnicity	n (%)	n (%)	n (%)
Asian	4043 (8.43)	5810 (12.7)	9853 (10.51)
Black	4027 (8.4)	4742 (10.36)	8769 (9.36)
Multiple	242 (0.5)	190 (0.42)	432 (0.46)
Native Am/Alaskan	152 (0.32)	127 (0.28)	279 (0.3)
Others	340 (0.71)	432 (0.94)	772 (0.82)
Pacific Islander	728 (1.52)	691 (1.51)	1419 (1.51)
Unknown	1107 (2.31)	829 (1.81)	1936 (2.07)
White	14,482 (30.19)	7914 (17.29)	22,396 (23.89)
Hispanic	22,843 (47.63)	25,031 (54.69)	47,874 (51.08)
Had type 2 diabetes history prior to the first dose	n (%)	n (%)	n (%)
No	9851 (20.54)	10,094 (22.06)	19,945 (21.28)
Yes	38,113 (79.46)	35,672 (77.94)	73,785 (78.72)
Had AMI history between 01/01/2010 to first dose date	n (%)	n (%)	n (%)
No	47,359 (98.74)	45,260 (98.89)	92,619 (98.81)
Yes	605 (1.26)	506 (1.11)	1111 (1.19)
Had hospitalized AMI in 12 months after first dose date	n (%)	n (%)	n (%)
No	47,891 (99.85)	45,713 (99.88)	93,604 (99.87)
Yes	73 (0.15)	53 (0.12)	126 (0.13)

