6.0 STUDY METHODS

6.1 Exposure of Interest

The exposure of interest for this study is the index dose of hepatitis B vaccine (Section 4.2).

Hepatitis B vaccine exposure will be assigned at the cluster level. At target medical centers, providers in family practice and internal medicine departments will only be able to order HEPLISAV-B for hepatitis B vaccination of adult patients not on dialysis. Patients receiving an index dose of HEPLISAV-B in family practice or internal medicine departments will be included in the HEPLISAV-B cohort.

At non-target medical centers, providers in family practice or internal medicine departments will only be able to order a hepatitis B comparator vaccine other than HEPLISAV-B. Only patients receiving an index dose of comparator vaccine in family practice or internal medicine departments will be included in the comparator cohort. In recent years at KPSC, Engerix-B has been used for routine vaccination, while Recombivax-HB (Dialysis Formulation) has been used for dialysis patients. As dialysis patients are not included in this study, the comparator is expected to be Engerix-B.

Adults vaccinated with one or more doses of comparator hepatitis B vaccine prior to study initiation who did not complete the full 3-dose regimen may be given HEPLISAV-B if they

receive care at a HEPLISAV-B target medical center. These patients will be included in the primary analysis, while exploratory analyses will seek to identify differential outcomes between these patients and those who received their first dose of hepatitis B vaccine during the study period (Section 7.6).

While providers are advised to follow ACIP and RIPC recommendations, decisions regarding the appropriateness of administering a hepatitis B vaccination and the vaccination schedule will be determined by the healthcare providers and patients. Vaccine exposure will be identified retrospectively from the electronic health records, including vaccine, dose, manufacturer, and lot number entered at the time of vaccination. Data on vaccine exposure will be checked using quality control procedures described in Section 8.2 below.

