7.3 Primary Analysis

For the final analysis of the primary objective, we will use a non-inferiority framework to test the null hypothesis of increased risk of Type 1 AMI among HEPLISAV-B recipients versus comparator vaccine recipients. Based on anticipated number of confirmed events, the study will have approximately 87% power to exclude a hazard ratio of 2.0 or greater (Section 7.9), testing the hypothesis: H_0 : $HR \ge 2$, H_a : HR < 2.

The rates of occurrence of first Type 1 AMI event during the study period among HEPLISAV-B recipients and comparator vaccine recipients will be compared using a Cox proportional hazards regression model employing inverse probability of treatment weighting (IPTW)^[33]. The IPTW provides an assessment of the closeness of match in the weighted analysis across all variables, providing a sense of the degree of control of imbalance between the vaccine exposure groups. Two tables will be created comparing the cohort of HEPLISAV-B recipients to the cohort of recipients of the comparator vaccine. The first table will be unweighted, showing the true distribution of recipient characteristics. The second table will be weighted by the inverse probability of treatment as estimated by a propensity score model. Standardized difference scores will be used to assess whether balance of covariates is achieved between the cohorts. These 2 tables will show the effectiveness of the weighting at reducing effective differences between the cohorts.

The primary analysis will be conducted on confirmed Type 1 AMIs. Variables to consider in the propensity model are listed in Section 6.3. The primary exposure will be vaccine group

(HEPLISAV-B vs. comparator vaccine), and the outcome will be confirmed AMI. Clustering by medical center will be considered through random effects variables representing medical center. Censoring events will include end of study, disenrollment from Kaiser Foundation Health Plan (allowing for a 31-day gap in membership), and death from causes other than AMI. A hazard ratio of AMI for HEPLISAV-B versus the comparator vaccine, adjusted for potential confounding factors, and associated 95% confidence interval will be reported.

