7.5 Secondary Analysis

A secondary analysis will be conducted comparing the rates of occurrence of Type 1 unconfirmed AMI in the principal discharge diagnosis position in the HEPLISAV-B group to a historical group of patients from the HEPLISAV-B medical centers who received comparator vaccine in 2016. Patients ages 18 years and older will be included in the historical comparison group if they were vaccinated with non-dialysis formulation hepatitis B vaccine from 01 January 2016 to 31 December 2016 in KPSC family practice and internal medicine departments included in the HEPLISAV-B group in the post-licensure safety study and were KPSC members on the day of vaccination. Patients receiving chronic dialysis in the 3 months prior to hepatitis B vaccination will be excluded. In the unlikely event that someone receives vaccine in both time periods, they will only be included in the HEPLISAV-B cohort. Relative risk will be estimated using a Cox proportional hazards regression model with IPTW to adjust for differences in the populations, as described in Section 6.3.

If this comparison shows a significantly elevated risk for the HEPLISAV-B group, additional analyses will be performed in order to further investigate the elevated risk. We will graphically investigate the timing of the events relative to vaccination. We will perform sensitivity analyses by first dose vs. subsequent dose of hepatitis B vaccine and by concomitant vaccination status.

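### Before HEPLISAV-B, crude AMI risk at the target centers was 0.76 times that at comparator centers (95% CI 0.53 to 1.08); this does not support the claim of similar risk, and no planned analysis checks for a residual center offset together with calendar-time change

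*Protocol*

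**What the plan says.** Section 6.1: "Hepatitis B vaccine exposure will be assigned at the cluster level". Section 4.3: "Site selection for the study is based on clustering of medical centers and logistics"; proximity to the research headquarters and the places where clinical investigators work also count. The same section then reports that "The recipients in both the target and comparator medical centers had similar risk of AMI in the 12 months" after the first dose. The supporting row of Table 4-1 is "Had hospitalized AMI in 12 months after first dose date": 53 (0.12%) of 45,766 recipients at the 7 target centers and 73 (0.15%) of 47,964 at the 8 comparator centers.

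The primary analysis (Section 7.3) is a Cox model with IPTW on the patient covariates of Section 6.3, with medical center considered as a random effect. Power (Section 7.9) is computed on the assumption of equal AMI risk in the two groups.

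The secondary analysis (Section 7.5) compares HEPLISAV-B recipients with "a historical group of patients from the HEPLISAV-B medical centers who received comparator vaccine in 2016", on unconfirmed principal-position Type 1 AMI. It adds: "In the unlikely event that someone receives vaccine in both time periods, they will only be included in the HEPLISAV-B cohort".

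**The concern.** With vaccine fixed by center, any difference in AMI risk or AMI capture between the two sets of centers goes into the hazard ratio unless the patient covariates explain it. The 2015 row is the only pre-study check of this in the protocol. Its point estimate lies in the direction that would make HEPLISAV-B look safer. A random center effect cannot remove such an offset, because vaccine does not vary within a center.

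Section 6.4 itself allows that the share of events derived from claims may differ between target and comparator centers, and Section 4.3 puts about 45% of persons with AMI in claims. The 3-month lag deals with late claims, not with lasting differences in capture.

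The two planned comparisons have complementary gaps. The concurrent one is exposed to center differences. The historical one, within the target centers, cancels stable center differences but is exposed to change between 2016 and the study period. At stake is the central claim, exclusion of a hazard ratio of 2.0.

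**Working it through.** **1. The plan's own power.** Inputs from Section 7.9: 78 events, margin 2.0, one-sided alpha 0.025, equal groups, true HR 1.

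Power = Φ(√(78/4) × ln 2 − 1.96) = Φ(4.416 × 0.693 − 1.96) = 0.865. Table 7-1 gives 0.865, so it reproduces.

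**2. The 2015 risks (Table 4-1).**

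- Target: 53/45,766 = 1.16 per 1000. Comparator: 73/47,964 = 1.52 per 1000. Ratio 0.761.
- SE of the log ratio = √(1/53 − 1/45,766 + 1/73 − 1/47,964) = 0.180.
- 95% CI = exp(−0.273 ± 1.96 × 0.180) = 0.53 to 1.08; p = 0.13 (chi-square without correction, and Fisher).
- With 126 events, power to detect a true ratio of 0.76 (two-sided 5%) is about 33%. The row can establish neither a difference nor similarity.

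**3. Measured differences in the same table.**

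- Prior AMI: 506/45,766 (1.11%) against 605/47,964 (1.26%), ratio 0.88 (95% CI 0.78 to 0.99).
- White recipients: 17.3% against 30.2%, standardized difference −0.31.
- Both are candidate covariates, so IPTW may remove some or all of the gap. The documents do not allow the adjusted ratio to be computed.

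**4. Effect of a residual offset.** Assume an offset b remains after adjustment, so that a true HR appears as b × HR. The probability of excluding 2.0 is Φ(4.416 × ln(2/(b × HR)) − 1.96).

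| Residual offset b | Wrongly excludes 2.0 when true HR is 2.0 | Power when true HR is 1 |
|---|---|---|
| 1.00 (plan) | 2.5% | 86% |
| 0.95 | 4% | 91% |
| 0.90 | 7% | 94% |
| 0.85 | 11% | 97% |
| 0.76 (crude ratio, unadjusted) | 23% | 99% |
| 1.08 (upper CI limit) | 1% | 77% |

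Worked line for 0.76: Φ(4.416 × 0.273 − 1.96) = Φ(−0.75) = 0.23.

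**5. Precision of a ratio of hazard ratios.** Assume 78 study-period events, 126 historical events for 2015, and 15% fewer (107) for 2016, following the decline in doses given in Section 7.9.

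- Study-period HR alone: 2/√78 = 0.226.
- Ratio with 2016 only: √(4/78 + 4/107) = 0.30.
- Ratio with 2015 and 2016: √(4/78 + 4/233) = 0.26.

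Table 4-1 counts hospitalized AMI and does not say that it is limited to the principal position, so event numbers under the Section 7.5 endpoint may differ.

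**6. The overlap rule in Section 7.5.** A person vaccinated in 2016 and again in the study period must have survived and stayed a member in between. Removing such people from the historical cohort takes out person-time that is free of fatal AMI, which tends to raise the historical rate and lower the HR. The protocol gives no count of these people and expects few. It does, however, provide for HEPLISAV-B in people with an incomplete earlier series (Sections 6.1 and 7.6). The size cannot be derived.

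**The case against.** A reader might infer from Table 4-1 that a bias favoring HEPLISAV-B is established, cannot be removed, and raises the false-exclusion rate to 23%. The documents do not support that:

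- The ratio is crude and its interval includes 1.
- Section 6.3 lists a broad set of covariates, Section 7.3 requires balance tables before and after weighting, and the visible imbalances point the same way as the AMI gap.
- The primary outcome is definite or probable Type 1 AMI adjudicated by masked cardiologists (Sections 6.2.2 and 6.2.3), and missing outside records are sought (Section 6.4). Differences in coding therefore matter less than for the coded events that the table appears to count.
- Table 4-1 states neither the dialysis exclusion nor the department restriction of the study.
- Section 7.8 reports an intra-class correlation below .00001 for 2015. With 15 centers and 126 events this is weak evidence, but it does not point to a center effect.

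Nor is the target-only historical cohort the cause of the problem. It is a partial remedy, because it cancels stable center differences.

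All of this stands, and it limits the point to a possible bias that is not checked. It does not rescue the statement of similar risk. Nor does it supply a comparison that handles center and calendar time together: IPTW balances measured patient characteristics only, and cases without adequate records are classed as unable to determine (Section 8.1) and so fall outside the primary outcome.

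Supportive analyses often sit in the SAP, which is not shown. But the statement of similar risk, the reach of the historical cohort and the overlap rule are all fixed in the protocol.

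**Conclusion.** The point holds as a limited one. The 2015 data give a crude ratio of 0.76 (0.53 to 1.08), which supports neither similar risk nor a proven offset. Because exposure is fixed by center, a modest residual offset matters: 0.90 would take the false-exclusion rate from 2.5% to about 7%. The 23% figure requires the whole crude gap to survive weighting and adjudication, and an offset in the other direction would make the test conservative, at about 1% with power 77%. These figures assume 78 events, equal groups and a constant multiplicative offset. The overlap rule in Section 7.5 is a separate flaw of known direction and unknown, possibly small, size. None of this requires a change to the primary analysis; a supportive check should be added.

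**What to change.** 1. In Section 4.3, replace the statement of similar risk with the observed ratio and its interval: 0.76 (95% CI 0.53 to 1.08).
2. Extend the Section 7.5 historical cohort to recipients at the 8 comparator centers. Fit the same IPTW Cox model to target versus comparator centers in that period, when no center used HEPLISAV-B and the expected HR is 1. Report that HR, and the ratio of the study-period HR to it with a 95% CI, as a supportive analysis. Use unconfirmed principal-position Type 1 AMI in both periods; this is already the endpoint of Section 7.5 and of the final unconfirmed analysis in Section 7.1. Dividing the adjudicated primary HR by an unadjudicated historical HR would mix outcomes.
3. Keep patients vaccinated in both periods in both cohorts, with person-level robust variance.

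Cost: one more extract from the same data warehouse and a rerun of the code, with no extra adjudication. The interval is wider (SE of the log ratio about 0.26 to 0.30 against 0.23), so the result supports the primary HR and does not replace it.
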